### **4.2. Extent of Exposure**

#### **4.2.1. Duration of Exposure to Study Regimen**

Duration of exposure to study regimen will be defined as (last dose date of any study drug – first dose date of any study drug + 1), regardless of temporary interruptions in study drug administration and will be expressed in weeks (recorded to 1 decimal place, eg, 12.1 weeks). For subjects ongoing at the time of an analysis, the last dosing date will be estimated based on the last available eCRF or laboratory date available in the snapshot database.

Duration of exposure to study regimen will be summarized using descriptive statistics (sample size, mean, standard deviation [SD], median, first quartile [Q1], third quartile [Q3],

minimum and maximum) and as the number of subjects exposed *through* (ie, cumulative counts): Baseline (Day 1); Week 1 (Day 7); Week 2 (Day 14); Week 4 (Day 28); Week 6 (Day 42); Week 8 (Day 56); Week 10 (Day 70); Week 12 (Day 84); Week 16 (Day 112); Week 20 (Day 140); Week 24 (Day 168).

Summaries will be provided by treatment group for the safety analysis set.

## 5. BASELINE DATA

### 5.1. Demographics and Baseline Characteristics

The following subject demographic and baseline characteristics will be summarized by treatment group and overall using descriptive statistics (sample size, mean, standard deviation, median, Q1, Q3, minimum and maximum) for continuous data and by the number and percent of subjects for categorical data. Variables to be summarized include the following:

- age (on date of first dose of study regimen) as a continuous variable
- sex (male, female)
- race
- ethnicity (hispanic or latino, non-hispanic or latino)
- body mass index as a continuous variable and for categories ( $< 30 \text{ kg/m}^2$ ,  $\geq 30 \text{ kg/m}^2$ )
- HCV genotype (1, 2, 3)
- cirrhosis (yes/no)
- IL28B (CC, CT, TT)
- baseline HCV RNA as a continuous variable and for categories ( $< 6 \log_{10} \text{ IU/mL}$ ,  $\geq 6 \log_{10} \text{ IU/mL}$ )
- baseline ALT as a continuous variable and for categories ( $\leq 1.5 \times \text{ULN}$ ,  $> 1.5 \times \text{ULN}$ )
- estimated glomerular filtration rate (eGFR) using Cockcroft-Gault formula
- CD4 counts at baseline as a continuous variable and for categories ( $< 200 \text{ cells/mm}^3$ ,  $200 \text{ cells/mm}^3 \leq \text{CD4 count} < 350 \text{ cells/mm}^3$ ,  $350 \text{ cells/mm}^3 \leq \text{CD4 count} \leq 500 \text{ cells/mm}^3$ , or  $> 500 \text{ cells/mm}^3$ )
- on ARV treatment at enrollment (yes, no)
- ARV regimen at enrollment
- interferon classification (IFN-eligible, IFN-ineligible, IFN-intolerant, non-response, relapse/breakthrough)

Age is calculated as the integer of age in years at first dose of study regimen for subjects dosed and calculated as the integer of age in years at enrollment for subjects enrolled but not dosed. eGFR will be calculated by the Cockcroft-Gault method:  $eGFR_{CG} \text{ (mL/min)} = [(140 - \text{age (yrs)}) \times \text{weight (kg)} \times (0.85 \text{ if female})] / (\text{serum creatinine (mg/dL)} \times 72)$ , where weight is total body mass in kilograms..

The summary of demographic data and baseline characteristics will be provided for the safety analysis set.

In addition, number and percentage of subjects for each interferon ineligibility reason and number and percentage of subjects for each interferon intolerant reason will be provided. The denominator for the percentages will be the number of subjects in safety analysis set who are interferon ineligible and number of subjects in safety analysis set who are interferon intolerant, respectively.

## **5.2. Medical History**

General medical history (ie, conditions not specific to the disease being studied) data will be listed only. General medical history data will not be coded.

## 6. EFFICACY ANALYSES

### 6.1. Definition of the Efficacy Endpoints

The efficacy endpoints for this safety update include the following:

- SVR12 defined as HCV RNA < LLOQ (ie, < 25 IU/mL) at 12 weeks after study drug cessation for the full analysis set. The Roche COBAS® Taqman® HCV Test v2.0 for use with the High Pure System will be used to measure HCV RNA.
- Sustained virologic response 4 weeks after stopping all study drugs (SVR4) defined as HCV RNA < LLOQ (ie, < 25 IU/mL) at 4 weeks after study drug cessation for the full analysis set
- The proportion of subjects with HCV RNA below LLOQ (ie, < 25 IU/mL) while on treatment by study visit
- The proportion of subjects with on-treatment and posttreatment virologic failure, defined as the following:
  - On-treatment virologic failures
    - HCV RNA  $\geq$  25 IU/mL after having previously had HCV RNA < 25 IU/mL while on treatment, confirmed with 2 consecutive values (Note: second confirmation value can be posttreatment) or last available on-treatment measurement with no subsequent follow-up values (ie, breakthrough)
    - $>1 \log_{10}$  IU/mL increase in HCV RNA from nadir while on treatment, confirmed with 2 consecutive values (Note: second confirmation value can be posttreatment) or last available on-treatment measurement with no subsequent follow up values (ie, rebound)
    - HCV RNA persistently  $\geq$  25 IU/mL through 8 weeks of treatment (ie, nonresponse)
  - Relapse
    - HCV RNA  $\geq$  25 IU/mL during the posttreatment period having achieved HCV RNA < 25 IU/mL at end of treatment, confirmed with 2 consecutive values or last available posttreatment measurement

### 6.2. Analysis of the Efficacy Endpoint

The efficacy endpoints will be derived for all subjects in safety analysis set using observed HCV RNA data and imputation rule specified in section 3.6.

For analyses of HCV RNA < LLOQ (ie, < 25 IU/mL) by visit while on treatment, subjects will be assigned a value at each visit based on the categorical imputation rules described in Section **Error! Reference source not found.** The 2-sided 95% exact confidence interval (CI) based on Clopper-Pearson method will be provided for the proportion {20839}. The overall category for “HCV RNA < LLOQ” will be split into the following 2 subcategories: “< LLOQ TND” for subjects with target not detected and “< LLOQ detected” for subjects with < LLOQ in tabular displays.

The point estimate of SVR4 and SVR12 rate and 2-sided 95% exact confidence interval (CI) will be provided for each treatment group and for each treatment group within each subgroup specified in section 3.4. A Forest plot will graphically present estimates and 95% confidence intervals of SVR4 and SVR12 rates for each treatment group within each subgroup.

For the SVR12 endpoint analysis, a summary table of the number and percentage of subjects with SVR12, virologic failure, and other will be created. All subjects who achieve SVR12 will be categorized as SVR12. Virologic failure will be descriptively summarized as “on-treatment virologic failure” and relapse (which will be summarized by study drug completed yes or no). Subjects who do not achieve SVR12 and do not meet criteria for virologic failure will be categorized as other. The denominator for relapse will be the number of subjects who had HCV RNA < LLOQ on their last observed on-treatment HCV RNA measurement; otherwise, the denominator will be the number of subjects in the FAS.

Details regarding SAS programming are provided in the programming specifications in **Error! Reference source not found.** of this SAP.

A data listing of HCV genotype, cirrhosis, IL28B, scheduled visit, analysis visit window, date of HCV RNA sample collection, HCV RNA load (categorical and numeric), and change from baseline for on-treatment visits will be provided for the following:

- 1), subjects with HCV virologic failure in the FAS;
- 2), all subjects in the FAS
- 3), all subjects in the safety analysis set but not in FAS

## **7. SAFETY ANALYSES**

Safety data will be summarized for subjects included in the safety analysis set. Summaries of safety data (treatment-emergent [TE] adverse events [AEs], TE maximum toxicity grades and marked abnormalities, changes from baseline in laboratory and vital signs parameters) will include all data collected on or after the first dose date of study regimen through the last dose date of any study drug plus 30 days (except HIV RNA and CD4 data, which is through the end of study) for subjects who have stopped all study drugs, and all available data at the time of the database snapshot for subjects still on treatment at the time of this analysis.

All safety data (except for laboratory tests with results that were cancelled by the lab) will be included in data listings based on the safety analysis set.

### **7.1. Adverse Events**

#### **7.1.1. Adverse Event Dictionary**

Clinical and laboratory AEs will be coded using the Medical Dictionary for Regulatory Activities (MedDRA). System organ class (SOC), high level group term (HLGT), high level term (HLT), preferred term (PT), and lower level term (LLT) will be attached to the clinical database.

#### **7.1.2. Adverse Event Severity**

Adverse events are graded by the investigator according to the Gilead Sciences, Inc. (Gilead) Grading Scale for Severity of Adverse Events and Laboratory Abnormalities as specified in the clinical study protocol. The severity grade of events for which the investigator did not record severity will be categorized as “missing” for tabular summaries and data listings, and will be considered the least severe for the purposes of sorting for data presentation.

#### **7.1.3. Relationship of Adverse Events to Study Drug**

The relationship of AE to study drug will be assessed by investigators as “Yes” or “No”. Events for which the investigator did not record the relationship to study drug will be considered to be related to study drug for summary purposes. However, data listings will present the relationship as missing.

#### **7.1.4. Serious Adverse Events**

Serious adverse events (SAEs) are those identified as serious in the clinical database. The clinical database will be reconciled with the SAE database from the Drug Safety and Public Health Department before database finalization.

### **7.1.5. Treatment-Emergent Adverse Events**

#### 7.1.5.1. Definition of Treatment-Emergent

Treatment-emergent AEs are events that meet one of the following criteria:

- Events with onset dates on or after the start of treatment and up to 30 days after the permanent discontinuation of all the study medications,
- The continuing adverse events diagnosed prior to the start of treatment and worsening in severity grade, or non-serious adverse events at baseline which become serious, or adverse events resulting in treatment discontinuation after the start of treatment

#### 7.1.5.2. Incomplete Dates

If the date of onset is incomplete, then the month and year (or year alone if month is not recorded) of onset determine whether the AE is treatment emergent. The event is treatment emergent if the month and year of onset (or year of onset) of the event meets both of the following criteria:

- The same as or after the month and year (or year) of the first dose of any study drug
- The same as or before the month and year (or year) of the 30th day after the date of the last dose of any study drug

### **7.1.6. Summaries of Adverse Events and Deaths**

A brief summary of AEs will show, by treatment group, the number and percentage of subjects who (1) had any TE AE, (2) had any Grade 3 or higher TE AE, (3) had any Grade 2 or higher TE AE, (4) had any TE treatment-related AE, (5) had any Grade 3 or higher TE treatment-related AE, (6) had any Grade 2 or higher TE treatment-related AE, (7) had any TE SAE, (8) had any TE treatment-related SAE, (9) had any AE leading to permanent discontinuation from any study drug, (10) had any AE leading to permanent discontinuation from SOF, (11) had any AE leading to modification or interruption of any of the drugs, and (12) TE death during the study.

Summaries (number and percentage of subjects) of adverse events (by SOC and PT) will be provided using the safety analysis set as follows:

- All TE AEs
- Combined Grade 3 or 4 TE AEs
- TE non-serious AEs occurring in at least 5% of subjects in any treatment group (this will be produced for ClinicalTrials.gov website)

- TE AEs treatment-related drug
- Combined Grade 3 or 4 TE treatment-related AEs
- TE SAEs
- TE treatment-related SAEs
- AEs leading to permanent discontinuation from any of the study drugs
- AEs leading to permanent discontinuation from SOF

Multiple events will be counted once only per subject in each summary. For data presentation, SOC will be ordered alphabetically, with PT sorted by decreasing total frequency within an SOC. For summaries by severity grade, the most severe event will be selected.

Data listings, with a variable indicating whether the event is treatment-emergent, will be provided for the following:

- All AEs
- SAEs
- Deaths
- AEs leading to permanent discontinuation of any of the study drugs
- AEs leading to permanent discontinuation from SOF
- Grade 3 or 4 Adverse Events

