## 6. STUDY PROCEDURES

All subjects will complete screening, on-treatment and post-treatment assessments. All subjects will complete a 4-week Post-Treatment visit regardless of the treatment duration. Subjects with HCV RNA < LLOQ at the end of treatment and 4-Week Post-Treatment visit will complete 12-week and 24-week Post-Treatment visits unless confirmed viral relapse occurs. Completion of the study will occur at the 24-Week Post-Treatment visit.

The schedule of assessments is provided below. Details of the study procedures to be conducted for each subject enrolled in the study are presented in Study Procedures Table located in [Appendix 2](#). Information on the specific laboratory parameters to be measured and clinical assessments to be performed are provided in Section [6.4](#).

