### **8.4.3. Reporting Requirements**

All AEs, regardless of causal relationship, must be reported for subjects on treatment and through the 4-Week Post-Treatment Visit.

All SAEs, including deaths, regardless of causal relationship, must be reported from signing of the informed consent through the end of the study. Investigators are not obligated to actively seek SAEs beyond this point. However, if the investigator learns of any SAEs that occur after study participation and the event is deemed relevant to the use of investigational medicinal product(s), he/she should promptly document and report the event to the CRO Pharmacovigilance Representative or to Gilead Sciences, DSPH if the study has been completed. Gilead DSPH contact information is as follows: Email: Safety\[contact] and [contact].

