## Appendix 1. Table of Contents for Statistical Tables, Figures, and Listings

Table Number	Title	Analysis Set
1	Subject Disposition	Screened Subjects
2	Demographics and Baseline Characteristics	Safety Analysis Set
3.1	Summary of Interferon Ineligible Reason	Safety Analysis Set
3.2	Summary of Interferon Intolerant Reason	Safety Analysis Set
4	Duration of Exposure to Study Regimen	Safety Analysis Set
5	HCV Virologic Outcome	Full Analysis Set
6	SVR by Visit during Posttreatment Follow Up (SVR4 and SVR12)	Full Analysis Set
6.1	SVR by Visit during Posttreatment Follow Up (SVR4 and SVR12) by Subgroup	Full Analysis Set
7	Proportion of subjects with HCV RNA Less than LLOQ (25 IU/mL) While on Treatment by Visit	Full Analysis Set
8	Adverse Events: Brief Summary	Safety Analysis Set
9	All Treatment-Emergent Adverse Events	Safety Analysis Set
10	Treatment-Emergent Treatment-Related Adverse Events	Safety Analysis Set
11	Grade 3 or 4 Treatment-Emergent Adverse Events	Safety Analysis Set
12	Grade 3 or 4 Treatment-Emergent Treatment-Related Adverse Events	Safety Analysis Set
13	Adverse Events Leading to Permanent Discontinuation from Any of the Study Drugs	Safety Analysis Set
14	Adverse Events Leading to Permanent Discontinuation from SOF	Safety Analysis Set
15	Treatment-Emergent Serious Adverse Events	Safety Analysis Set
16	Treatment-Emergent Treatment-Related Serious Adverse Events	Safety Analysis Set
17	Treatment-Emergent Non-Serious Adverse Events Occurring in At Least 5% of Subjects in Any Treatment Group	Safety Analysis Set
18.1	ALT (U/L) and Change from Baseline by Visit	Safety Analysis Set
18.2	AST (U/L) and Change from Baseline by Visit	Safety Analysis Set
18.3	Total Bilirubin (mg/dL) and Change from Baseline by Visit	Safety Analysis Set
18.4	Alkaline Phosphatase (U/L) and Change from Baseline by Visit	Safety Analysis Set
18.5	WBC ( $\times 10^3/\mu\text{L}$ ) and Change from Baseline by Visit	Safety Analysis Set
18.6	Neutrophils ( $\times 10^3/\mu\text{L}$ ) and Change from Baseline by Visit	Safety Analysis Set
18.7	Lymphocytes ( $\times 10^3/\mu\text{L}$ ) and Change from Baseline by Visit	Safety Analysis Set

Table Number	Title	Analysis Set
18.8	Hemoglobin (g/dL) and Change from Baseline by Visit	Safety Analysis Set
18.9	Platelets ( $\times 10^3/\mu\text{L}$ ) and Change from Baseline by Visit	Safety Analysis Set
18.10	Reticulocytes ( $\times 10^3/\mu\text{L}$ ) and Change from Baseline by Visit	Safety Analysis Set

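### SAP 7.1.6 and Table 8 count deaths and SAEs only if treatment-emergent, although both are collected to the end of the study, and a treatment-emergent death is not defined

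*Combined protocol and SAP*

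**What the plan says.** **Collection.** Protocol 8.4.3 states: "All SAEs, including deaths, regardless of causal relationship, must be reported from signing of the informed consent through the end of the study". Protocol 6 fixes the end point: "Completion of the study will occur at the 24-Week Post-Treatment visit".

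**Tabulation.** SAP 7 includes safety data in summaries "through the last dose date of any study drug plus 30 days" for subjects who have stopped all study drugs. HIV RNA and CD4 are the stated exceptions and run to the end of the study. SAP 7.1.5.1 defines a treatment-emergent AE mainly by onset, "up to 30 days after the permanent discontinuation of all the study medications".

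**Counts.** In the brief summary of SAP 7.1.6 (Table 8), the SAE items are "7) had any TE SAE, (8) had any TE treatment-related SAE" and the death item is "and (12) TE death during the study". The SAE tables by SOC and PT are Table 15 and Table 16, the latter titled "Treatment-Emergent Treatment-Related Serious Adverse Events". Appendix 1 of the SAP has no deaths table and no table of all SAEs.

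**Listings.** SAP 7.1.6 lists all AEs, all SAEs and all deaths, each with a variable showing whether the event is treatment-emergent. These are Listings 8, 12 and 14.

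**The concern.** Safety is a primary objective of the trial, to be judged from the accumulated safety data. The summary table is where most readers will look for deaths. Its death row is worded as covering the study but closes 30 days after the last dose. If a subject died in follow-up from an event that began after day 30, the row could show zero even though the death had been reported as the protocol requires. With about 230 subjects planned, a single death decides between zero and one.

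There is also a problem of definition. Protocol 8.3 treats death as the outcome of an AE and not as an AE, while SAP 7.1.5.1 defines treatment-emergence only for AEs. The SAP does not carry the term over to deaths, so two programmers could produce different counts from the same data.

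**Working it through.** The plan gives no figure on this point, so there is none to reproduce. The check sets collection against tabulation and measures the gap.

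**Inputs**
- End of tabulation window: last dose + 30 days (SAP 7 and 7.1.5.1).
- End of collection: post-treatment Week 24 (protocol 6 and 8.4.3), nominal day 24 × 7 = 168 after last dose.
- Follow-up required for this analysis: Groups 1 and 3 have completed post-treatment Week 12 or discontinued (SAP 2.1), nominal day 12 × 7 = 84.

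**Step 1: is any safety count open after day 30?** Items 7, 8 and 12 of the brief summary are treatment-emergent, and so are Tables 15 and 16. No other table in SAP Appendix 1 counts SAEs or deaths. Table 1 gives reasons for not completing the study (SAP 4.1). Death might be one of them, but the categories are not named and this is not a safety count.

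**Step 2: length of the uncounted period.** Uncounted days = last follow-up day − 30.

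| Followed to | Uncounted days | Number | Share of post-treatment time |
|---|---|---|---|
| Post-treatment Week 12 | 31 to 84 | 84 − 30 = 54 | 54/84 = 64% |
| Post-treatment Week 24 | 31 to 168 | 168 − 30 = 138 | 138/168 = 82% |

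Measured from first dose to post-treatment Week 12, the 54 days are 54/(84 + 84) = 32% in Group 1 and 54/(168 + 84) = 21% in Group 3.

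**Step 3: who contributes this time.** Under protocol 3.2 only subjects with HCV RNA below LLOQ at post-treatment Week 4 go on to Weeks 12 and 24. Those at or above LLOQ leave scheduled follow-up at about day 28, inside the 30-day window, and contribute little. The assumed SVR12 rates (62%, 40% and 65% in SAP 1.3) leave 38%, 60% and 35% of subjects without SVR12. How many of these would fail by Week 4 is not stated. Group 2 need not have reached any post-treatment visit at this analysis.

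**Step 4: what a treatment-emergent death is.** Suppose an SAE begins on day 20 after last dose and the subject dies on day 45. By the onset rule of SAP 7.1.5.1 the fatal event is treatment-emergent, and the death could be counted. By the data cut in SAP 7 the death falls after day 30 and would be left out. Both readings are open. If the fatal event begins on day 31 or later, neither reading counts the death unless the event falls under the second criterion of 7.1.5.1. That criterion covers pre-treatment events that worsen or become serious, and it states no upper time limit.

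**The case against.** The strongest reply is that the SAP does what the protocol asks. Protocol 9.5 sets the 30-day window, and 9.5.2 plans treatment-emergent summaries, with SAEs including death among them, plus listings of all AEs. This stands: a reader might infer a departure from the protocol, and there is none.

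A second reply is that no event is lost. A reader might infer that late deaths and SAEs go unreported. The documents do not support that, because Listings 8, 12 and 14 carry them by subject with the flag. What is missing is a count by group.

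A third reply concerns the HIV RNA and CD4 exception. Those tests are scheduled at post-treatment Weeks 12 and 24, whereas AE assessment is scheduled only at Week 4 (protocol 6.3 and Appendix 2 Table 3). The exception shows that end-of-study reporting is possible, but it is not a close parallel. After Week 4, SAEs remain reportable but no scheduled assessment elicits them, so an all-SAE row would combine events found in different ways. This weakens the case for that row. It has less force for deaths, which depend less on being asked about.

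Finally, this SAP serves only the EMEA 120-day response and AASLD analysis. A reader might apply the 138-day gap to everyone in it, but the analysis requires only Week 12 follow-up, and only in Groups 1 and 3.

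**Conclusion.** The point holds as a weakness in reporting. It biases no efficacy estimate and breaks no protocol commitment. Fatal and serious events with onset after last dose + 30 days are collected and listed but enter no safety count by group, and the death count that is planned rests on an undefined term.

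At this analysis the uncounted post-treatment time is at least 54 of 84 days for Group 1 and 3 subjects who reach Week 12, and up to 138 of 168 days for any followed to Week 24. These figures assume nominal visit days and apply to subjects who stay in follow-up, which after Week 4 means mainly HCV responders.

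Two stronger readings should be resisted. One is that every death after day 30 is left out: under the onset rule a death from an earlier event may be counted. The other is that late hepatic, HIV-related or malignancy events fall mostly in the uncounted period: the documents give no figure on the timing of such events. Any later final-analysis plan is not among the documents, so the conclusion is confined to this SAP.

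**What to change.** In SAP 7.1.6 and Table 8:

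1. Replace item 12 with all deaths from first dose to end of study or data cut, by treatment group, with a sub-row for treatment-emergent deaths. Name the cut date used.
2. State whether date of death or onset of the fatal AE makes a death treatment-emergent, and reconcile this with the data cut in SAP 7.
3. Optionally, add a row for all SAEs from first dose to end of study or data cut beside the treatment-emergent row. Footnote it with the number of subjects followed beyond day 30 in each group and the fact that no AE assessment is scheduled after post-treatment Week 4.

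Leave the treatment-emergent tables by SOC and PT as they are. The cost is one or two rows, one sentence of definition and, if the SAE row is added, a footnote. Listings 12 and 14 already need the data, so nothing new is collected. The one drawback is that the SAE row could be misread as a rate over uniform follow-up, which the footnote addresses.
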